Within 24 hours of admission to the inpatient floor, study subjects will be approached by a member of the research team, and asked for informed consent. Patients that consent to participate and meet our inclusion criteria will be ordered the appropriate study drug by the floor pharmacist, per the Yale Investigative Drug Service's randomization to either the treatment or the placebo arm. Each subject will be ordered a capsule containing either placebo (cellulose microcrystalline) or 5 mg melatonin each evening at 9 p.m. The study drug can be given as early as 7pm on the day of admission, if necessary, to allow treatment to begin within 24 hours of admission to the floor.. The capsules will be prepared and administered by the Yale-New haven Hospital Investigational Drug Service. The capsules will be administered nightly until discharge or a maximum of 2 weeks if the hospitalization is prolonged. The capsule must be swallowed whole and not opened.

Subjects will be assessed twice daily, once in the- a.m. and again in the p.m by the floor nurses for evidence of delirium using the Short CAM (Confusion Assessment Method), which is a validated clinical tool for identifying delirium, and the current standard of practice tool for the diagnosis of delirium. This evaluation should take maximally 5 to 10 minutes to complete.

While it is considered standard of care for nurses to administer the Short CAM once daily at Yale-New Haven Hospital, the twice daily Short CAM is standard of care at the University of Connecticut Hospital but not currently at the Yale-New Haven Health System with the exception of Verdi 4 West where the CAM is administered twice a day for all patients.

The primary endpoint will be the occurrence of delirium as defined by the Short CAM by the time of discharge or prior to hospital day 15, whichever occurs first. The study drug will be continued until the primary end point of delirium is reached, discharge or hospital day 15.

The maximum period of study drug administration will be 14 days. If the patient's length of stay exceeds 14 days the patient's participation in the study will end and the subject will be recorded as having completed the study without delirium. If the primary end point of delirium is reached, the subject will have completed the study, participation will be over and the study drug will no longer be administered.

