explanation that the subject may receive no direct benefit from participating but patient care may in general improve if the study drug successfully prevents delirium. If the patient is interested in enrolling then the patient is asked to remember 3 words (apple, penny, and table) and then is distracted by being asked to recite the days of the week backwards starting with Sunday. If the subject can remember at least 2 of the 3 words then the entire consent is reviewed in depth and the subject is asked if he understands and if he has any questions before signing. A “teach back” will be accomplished to insure that the subject or the surrogate understands all the research aspects of the study. A Short CAM will then be performed by the investigator to evaluate for delirium. If delirium is not diagnosed via the Short CAM, the consent form will be completed and the patient entered into the trial.

9. **Risks:** Describe the reasonably foreseeable risks, including risks to subject privacy, discomforts, or inconveniences associated with subjects participating in the research.

Minimal risks are anticipated with this study however participation in the study may involve risks that are currently not known. Possible risks include the swallowing of an extra pill and the lack of ability to take melatonin for impaired sleep. While Micromedex lists side effects of melatonin, such as tachyarrhythmia, red/flushed skin, hypothermia, decreased glucose tolerance, abdominal cramps/diarrhea, confusion, decreased reaction time, sedation, sleep pattern disturbance, and worsening of depression, these are considered rare and usually with little clinical effect. A recent review in the journal *Clinical Drug Investigations* (Andersen LP, Gögenur I, Rosenberg J, Reiter RJ. *Clin Drug Investig.* 2016 Mar;36(3):169-75. doi: 10.1007/s40261-015-0368-5. PMID:26692007) concluded that the short-term use of melatonin is safe, even in extreme doses and that only mild adverse effects have been reported and are probably no different than placebo²⁹, with the possible exception of sleepiness. Other potential adverse effects include dizziness, headache, and nausea as described below, in section VI.2. Melatonin should have no major drug interactions or effects on other possible drug interventions in our subjects. Mild to moderate interactions with warfarin, nifedipine and fluvoxamine are noted in Micromedex and patients treated with these medications will not be included in the study.

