The principal investigator is responsible for monitoring the data, assuring protocol compliance, and conducting the safety reviews at the specified frequency on a monthly basis. During the review process the principal investigator will evaluate whether the study should continue unchanged, require modification/amendment, or close to enrollment.

The principal investigator or the Institutional Review Board (IRB) have the authority to stop or suspend the study or require modifications.

This protocol presents minimal risks to the subjects and adverse events or other problems are not anticipated. In the unlikely event that such events occur, Reportable Adverse Events (which are events that are serious or life-threatening and unanticipated (or anticipated but occurring with a greater frequency than expected) and possibly, probably, or definitely related) or unanticipated problems involving risks to subjects or others will be reported in writing within 48 hours to

the IRB (using the appropriate forms from the website) and any appropriate funding and regulatory agencies. The investigator will apprise fellow investigators and study personnel of all adverse events that occur during the conduct of this research project through regular study meetings.

- d. For multi-site studies for which the Yale PI serves as the lead investigator:
- i. How will adverse events and unanticipated problems involving risks to subjects or others be reported, reviewed and managed?
 - ii. What provisions are in place for management of interim results?
 - iii. What will the multi-site process be for protocol modifications?

12. **Statistical Considerations:** Describe the statistical analyses that support the study design.
13.

Primary Outcome:

Incidence of delirium per admission of medical geriatric patients

Incidence of delirium per patient days of hospitalization in medical admission of geriatric patients

Secondary outcomes:

Risk factors associated with incident delirium

Duration of delirium by study group

Hospital length of stay

Sample size based was estimated using openepi.com (similar results with Stata version 14 sample size calculator) based on control group incidence of delirium in medical subgroup of 30%. (Chen et al: Exogenous melatonin for delirium prevention: a meta-analysis of randomized controlled trials - Molecular Neurobiology online publication 21 July 2015) with relative risk reduction of 30 %.

Sample Size: X-Sectional, Cohort, & Randomized Clinical Trials

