Two-sided significance level(1-alpha):	95
Power(1-beta, % chance of detecting):	80
Ratio of sample size, Unexposed/Exposed:	1
Percent of Unexposed with Outcome:	30
Percent of Exposed with Outcome:	21
Risk/Prevalence Ratio:	0.7
Risk/Prevalence difference:	-9

Sample size estimation by the Fleiss method yielded a total sample size of 734 with 367 in each group.

Descriptive statistics such as percentages for binary categorical variables, means and standard deviations for continuous variables. Fisher's exact test or chi-square test will be used to compare categorical variables. For continuous variables we will use t-test of unequal variances for means for normally distributed variables and the Wilcoxon-Mann-Whitney where normal distribution cannot be assumed. Risk ratio will be calculated using Stata statistical program version 14. (StataCorp LP, [name]) Associations with covariates will be tested using logistic regression with presence of incident delirium as the dependent variable.

Person days to delirium will be compared between the two groups using Survival analysis with Kaplan Meier curves, logrank test and Cox proportional hazards (covariates include age, comorbidities, medication numbers, presence of risk factors for delirium – polypharmacy, use of psychotropic or sedating medications, and use of bladder catheters).

Upon completing enrollment and analysis of 367 subjects, [name], a independent statistical expert, will analyze the data. In addition, an independent geriatrician expert in delirium will review any equivocal CAM results and make a decision as to the occurrence of delirium.

SECTION VI: RESEARCH INVOLVING DRUGS, BIOLOGICS, RADIOTRACERS, PLACEBOS AND DEVICES

If this section (or one of its parts, A or B) is not applicable, state N/A and delete the rest of the section.

A. DRUGS, BIOLOGICS and RADIOTRACERS

1. **Identification of Drug, Biologic or Radiotracer:** What is (are) the **name(s)** of the drug(s) biologic(s) or radiotracer(s) being used? Identify whether FDA approval has been granted and for what indication(s).

Melatonin—FDA categorized as a dietary supplement for sleep aid

All protocols which utilize a drug, biologic or radiotracer **not** approved by, but regulated by, the FDA, or a radiotracer regulated by the RDRC, must provide the following information:

a. What is the Investigational New Drug (IND) **number** assigned by the FDA?

FDA IND 129224-Melatonin

b. Who holds the IND?

[name]

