Consent must be obtained within 18 hours of the invitation to participate for the subject to be entered into the trial.

- 10. Evaluation of Subject(s) Capacity to Provide Informed Consent/Assent:** Indicate how the personnel obtaining consent will assess the potential subject's ability and capacity to consent to the research being proposed.

During the consent process, subjects will be asked to describe their understanding of the study, and given an opportunity to ask questions. If the investigator concludes that a subject lacks the capacity to consent, the medical decision maker of record will be approached for consent after the subject gives his/her affirmative assent..

- 11. Documentation of Consent/Assent:** Specify the documents that will be used during the consent/assent process. Copies of all documents should be appended to the protocol, in the same format that they will be given to subjects.

The subjects will receive the compound authorization and consent to enter the Melatonin to Prevent Delirium Study that will be reviewed by the study team personnel.

- 12. Non-English Speaking Subjects:** Explain provisions in place to ensure comprehension for research involving non-English speaking subjects. If enrollment of these subjects is anticipated, translated copies of all consent materials must be submitted for approval prior to use.

Non-English speaking subjects will not be included in the study

12(a) As a limited alternative to the above requirement, will you use the short form* for consenting process if you unexpectedly encounter a non-English speaking individual interested in study participation and the translation of the long form is not possible prior to intended enrollment?

YES NO
(not applicable)

Note* If more than 2 study participants are enrolled using a short form translated into the same language, then the full consent form should be translated into that language for use the next time a subject speaking that language is to be enrolled.

Several translated short form templates are found on our website at:

<http://www.yale.edu/hrpp/forms-templates/biomedical.html>. If the translation of the short form is not available on our website, then the translated short form needs to be submitted to the IRB office for approval via amendment prior to enrolling the subject. *Please review the guidance and presentation on use of the short form available on the HRPP website.*

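### The primary endpoint has no start point, so delirium found between trial entry and the first evening capsule counts as an event melatonin could not have prevented

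*Combined protocol and SAP*

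**What the plan says.** **Entry.** Section V.8 describes one Short CAM by the investigator during the consent process: "If delirium is not diagnosed via the Short CAM, the consent form will be completed and the patient entered into the trial". The exclusion criterion in Section V.7 is likewise judged at randomisation, not at the first dose.

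**Dosing.** Section V.3 schedules the capsule for 9 p.m. It may be given from 7 p.m. on the day of admission if needed, "to allow treatment to begin within 24 hours of admission to the floor".

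**Assessment.** Section V.3 has floor nurses perform the Short CAM twice daily, morning and p.m. It gives no clock times and does not name the first CAM that counts.

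**Endpoint.** Section V.3: "The primary endpoint will be the occurrence of delirium as defined by the Short CAM by the time of discharge", or before hospital day 15 if that is sooner. Reaching the endpoint ends participation and study drug.

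**Analysis.** Section V.12 lists delirium per admission and per patient-day as primary, and a survival analysis of person-days to delirium. It states no time origin, no analysis population and no rule for events before the first capsule.

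**Consent windows.** Section V.7 excludes patients who cannot consent within 18 hours of invitation or 24 hours of reaching the floor. Section VII.9 repeats the first limit: "Consent must be obtained within 18 hours of the invitation to participate for the subject to be entered into the trial".

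**The concern.** The stated aim (Section V.1) is prevention. Prevention can be observed only in people who are free of delirium when treatment starts. Here freedom from delirium is established at consent, treatment starts that evening or later, and at least one scheduled CAM can fall in between. A positive result on that CAM meets the endpoint as written, stops the drug before it has begun, and is counted in the assigned arm. Section V.2 describes delirium as fluctuating, so a single negative CAM can also miss an episode already under way that surfaces on the next assessment.

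These events occur at the same rate in both arms and cannot respond to melatonin. Counting them pulls the risk ratio toward 1 and costs power, and the sample size in Section V.12 states no allowance for this.

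**Working it through.** **1. The plan's own figure.** Inputs from Section V.12: control incidence 30%, relative risk reduction 30% (so 21% on melatonin), two-sided 5% level, 80% power, 1:1 allocation. The Fleiss formula without continuity correction, with p̄ = 0.255:

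n = [1.96·√(2·0.255·0.745) + 0.8416·√(0.30·0.70 + 0.21·0.79)]² / 0.09² = (1.2081 + 0.5160)² / 0.0081 ≈ 367 per arm.

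This matches the stated 367 per arm (734 in total). The calculation assumes that the risk ratio of 0.70 applies to every counted event.

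**2. Dilution when pre-dose events count.** Let f be the share of control-arm events that occur before the first capsule. The documents do not give f; the values below are assumptions. Pre-dose events occur at rate 0.30f in both arms, and 0.70 applies only to later events:

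melatonin rate = 0.30f + 0.21(1 − f)

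power = Φ{[Δ√n − 1.96√(2p̄(1 − p̄))] / √(p₁(1 − p₁) + p₂(1 − p₂))}, with n = 367, p₁ = 0.30, p₂ the melatonin rate, and Δ = p₁ − p₂.

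For f = 10%, p₂ = 0.030 + 0.189 = 0.219, Δ = 0.081 and p̄ = 0.2595. Power = Φ[(1.552 − 1.215)/0.617] = Φ(0.545) = 70.7%.

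| f | Pre-dose events, % of subjects | Melatonin rate | Observed RR | Power at 367 per arm | n per arm for 80% |
|---|---|---|---|---|---|
| 0 | 0 | 21.00% | 0.700 | 80.0% | 367 |
| 2% | 0.6 | 21.18% | 0.706 | 78.3% | 384 |
| 5% | 1.5 | 21.45% | 0.715 | 75.6% | 410 |
| 10% | 3.0 | 21.90% | 0.730 | 70.7% | 459 |

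**3. Counting only later events.** Among subjects still free of delirium at the first scheduled capsule, the control rate is 0.30(1 − f)/(1 − 0.30f), and the melatonin rate is 0.70 times that. The risk ratio returns to 0.70. Power depends on whether the subjects with pre-dose events are simply removed, leaving 367(1 − 0.30f) per arm, or replaced to keep 367:

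| f | Control rate | n per arm if removed | Power if removed | Power if replaced |
|---|---|---|---|---|
| 2% | 29.58% | 365 | 79.0% | 79.2% |
| 5% | 28.93% | 361 | 77.4% | 78.1% |
| 10% | 27.84% | 356 | 74.7% | 76.0% |

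Compared with step 2, the power recovered is about 1 to 4 points if removed and 1 to 5 points if replaced.

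**4. The timing statements side by side.** Take arrival on the floor at 3 p.m., invitation at 5 p.m. and consent at 11 a.m. the next day. Consent is 20 hours after arrival (within 24) and 18 hours after invitation (within 18), so the subject is eligible. The 7 p.m. allowance applies only to the day of admission, so the first capsule is at 9 p.m., 30 hours after arrival. The consent windows therefore admit subjects for whom the 24-hour start statement cannot be met. In this example the capsule comes 10 hours after the consent CAM.

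**The case against.** **The mechanism depends on CAM timing that is not stated.** If the p.m. CAM follows the capsule, it produces no pre-dose event. A reader might infer that morning-consented subjects routinely have a CAM before their first dose. The documents support only that they can.

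**The gap is probably short.** Consent spread evenly from 1 to 24 hours after floor arrival, at any hour of the day or night, gives a mean CAM-to-dose gap of about 12 hours, about half of starts after 24 hours, and a latest start near 48 hours. Limiting consent to 8 a.m. to 5 p.m. gives about 8.5 hours, 37% and 37 hours. Both sets of hours are assumptions, and the daytime one is more plausible.

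**A severe loss of power is not established.** At f = 20%, the observed risk ratio would be 0.76 and power 60%. That requires 6% of all randomised subjects, about 22 per arm, to turn positive within hours of a negative CAM, and nothing in the documents suggests it.

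**The comparison stays valid.** Counting from randomisation is a standard intention-to-treat choice. Type I error is unaffected and the arms remain balanced, so reading this as bias between arms would be wrong.

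**The planned effect may be conservative.** Section V.2 cites a medical-inpatient trial with 12% against 31%, a ratio of 0.39. Applied to later events with f = 10%, this gives 0.03 + 0.27·0.39 = 13.5%, an observed risk ratio of 0.45 and power above 99%. If the source trials counted events in the same way, some dilution may already be in the planning figures; the documents do not say.

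**There are some safeguards.** Section V.8 requires word recall and teach-back, and Section V.12 sends equivocal CAMs to an independent geriatrician.

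These points limit the size of the problem and show that re-timing randomisation is not essential. They do not supply the missing start point. Power also has to be judged at the 0.70 the plan chose. The geriatrician's review settles whether delirium occurred, not whether it came before treatment.

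**Conclusion.** The point holds as a modest, cheaply corrected weakness in the endpoint definition. As written, delirium between entry and the first capsule is a primary event that melatonin could not have prevented, and the resulting estimate of the preventive effect is diluted toward no effect. For assumed pre-dose shares of 2% to 10% of control events, the observed risk ratio is 0.706 to 0.73 instead of 0.70, and power is 78% to 71% instead of 80%. This rests on a true ratio of 0.70 for later events and equal pre-dose rates in both arms. The second follows from blinded randomisation with no drug yet given. At the lower end the loss is under 2 power points.

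The documents do not support a claim that the trial is biased, that its type I error is affected, or that an effective drug is likely to be missed for this reason alone. The conflict between the 24-hour start statement and the consent windows stands on the text, whatever the pre-dose share.

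**What to change.** 1. Define the primary endpoint as the first positive Short CAM after the time of the first scheduled capsule, and use that time as the origin for the person-days and survival analyses. Use the scheduled time, not actual ingestion, so that a refused capsule does not remove a subject. Apply the rule identically and blind in both arms; exclusion before any drug is given is then independent of allocation.
2. Report the count of all randomised subjects from randomisation as a pre-specified sensitivity analysis, with the number of pre-dose events by arm.
3. Optionally, where the p.m. CAM precedes the capsule and pharmacy workflow allows, assign the arm when the first capsule is released. The existing exclusion for delirium at randomisation then applies at the relevant moment, and affected subjects become screen failures who can be replaced. The documents establish neither the CAM timing nor evening cover by the Investigational Drug Service, so this is not a requirement.
4. Reconcile the 24-hour treatment-start statement in Section V.3 with the consent windows in Sections V.7 and VII.9.

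Items 1, 2 and 4 need wording changes and recorded times for each CAM and the first scheduled capsule, but no new assessment. The cost is the loss of a few pre-dose events or subjects: at f = 5%, 1.5% of subjects, or about 5 to 6 per arm (367 × 0.015 = 5.5). Item 3 would also need a CAM-timing rule on four floors and evening allocation by the pharmacy.

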Another possible risk involves potential breach of confidentiality with the collection of protected patient information. All patients in the study will be initially de-identified by use of medical record number and subsequently further de-identified by receiving a study number. Paper records will be kept in a locked office and computerized records will be kept in a secure hospital computer.

10. **Minimizing Risks:** Describe the manner in which the above-mentioned risks will be minimized.

Regarding the lack of ability to take melatonin for sleep; this risk is minimal, as melatonin is rarely used as a sleeping aid on the participating services. Currently only 7.2% of patients admitted to Celantano 3 and 12.3% of patients admitted to V4 West receive melatonin for

sleep. Clinicians will continue to treat insomnia with the usual non-pharmacologic and pharmacologic methods.

All patient data will be logged in a password protected YCCI / OnCore grid that will only be accessed by study personnel. All participants in the study will be HIPAA and HSPT trained.

The investigation team will review all patients, in EPIC or in person twice per day. Any possible complications will be followed closely.

11. **Data and Safety Monitoring Plan:** Include an appropriate Data and Safety Monitoring Plan (DSMP) based on the investigator's risk assessment stated below. (Note: the HIC will make the final determination of the risk to subjects.) For more information, see the Instructions, page 24.

- a. What is the investigator's assessment of the overall risk level for subjects participating in this study?

There is minimal risk anticipated for subjects participating in this study. Melatonin is considered a safe, over-the-counter, non-prescription supplement. A recent review²⁹ concluded that "Melatonin is safe for short-term use, even when given in extreme doses. Mild adverse effects, such as dizziness, headache, nausea and sleepiness have been reported in levels corresponding to placebo treatments." Section 9 lists Micromedex's side effect profile.

- b. If children are involved, what is the investigator's assessment of the overall risk level for the children participating in this study?

Not applicable

- c. Include an appropriate Data and Safety Monitoring Plan. Examples of DSMPs are available here <http://www.yale.edu/hrpp/forms-templates/biomedical.html> for

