Researchers are reminded that unauthorized disclosures of PHI to individuals outside of the Yale HIPAA-Covered entity must be accounted for in the "accounting for disclosures log", by subject name, purpose, date, recipients, and a description of information provided. Logs are to be forwarded to the Deputy HIPAA Privacy Officer.

7. **Required HIPAA Authorization:** If the research involves the creation, use or disclosure of protected health information (PHI), separate subject authorization is required under the HIPAA Privacy Rule. Indicate which of the following forms are being provided:

- Compound Consent and Authorization form
- HIPAA Research Authorization Form

8. **Consent Personnel:** List the names of all members of the research team who will be obtaining consent/assent.
9. **Process of Consent/Assent:** Describe the setting and conditions under which consent/assent will be obtained, including parental permission or surrogate permission and the steps taken to ensure subjects' independent decision-making.

Potential subjects will be approached by a member of the research team within 24 hours of their admission to the hospital. Care will be taken to explain the purpose of this study as well as potential risks associated with participation. If the subject wishes to proceed then the full consent form will be explained, and the potential subject will have opportunity and time to read the consent document on their own.

Given our elderly subject population, we anticipate that a percentage of our subjects will have cognitive deficits that will render them unable to provide their own informed consent. In those cases, in addition to requiring the subject's affirmative assent, the medical decision maker of record will be approached for informed consent. In such cases, the medical decision maker will be approached in person, if possible. If this is not possible, telephone consent witnessed and signed

by a member of the medical staff will be obtained.. The consent will be faxed to the surrogate if possible. All surrogates who give consent and are available to come to the hospital will be reconfirmed with written consent as soon as possible.

All subjects will be evaluated by the investigative team twice daily as long as they remain in the study. If subjects regain their capacity to give consent, such consent will be mandatory to their continuing in the study.

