Yes *If you answered yes, stop. A waiver cannot be granted.* Please note: Recruitment/screening is generally a minimal risk research activity

No

b. Will the waiver adversely affect subjects' rights and welfare? Yes No

c. Why would the research be impracticable to conduct without the waiver? The patients' names who are admitted to Celantano 3, Celantano 4, Verdi 5 West and Verdi 4 West and fit our inclusion criteria will be sent to the investigators via OnCore / EPIC. Before interviewing the patient we will need to review our exclusion criteria which can be done both via EPIC chart review and with discussion with the primary team. Once we are comfortable that the patient is a candidate for inclusion we will interview the patient and further review the inclusion and exclusion criteria and begin the invitation to consider participating in the study. By reviewing the chart and perhaps interviewing the care team we will avoid needlessly bothering some patients and be more efficient in our recruitment process.

d. Where appropriate, how will pertinent information be returned to, or shared with subjects at a later date? N/A

Requesting a full waiver of consent for the Entire Study (Note: If PHI is collected, information here must match Section VII, question 6.) N/A

If requesting a full waiver of consent, please address the following:

a. Does the research pose greater than minimal risk to subjects?

Yes *If you answered yes, stop. A waiver cannot be granted.*

No

b. Will the waiver adversely affect subjects' rights and welfare? Yes No

c. Why would the research be impracticable to conduct without the waiver?

d. Where appropriate, how will pertinent information be returned to, or shared with subjects at a later date?

SECTION VIII: PROTECTION OF RESEARCH SUBJECTS

Confidentiality & Security of Data:

a. What protected health information (medical information along with the HIPAA identifiers) about subjects will be collected and used for the research?

- Medical record number
- Date of Admission
- hyperactive delirium
- hypoactive delirium
- Length of stay
- Age
- Gender
- Primary diagnosis
- Secondary diagnosis
- Mortality
- Use of restraints
- # prn antipsychotic doses
- PRN sleep meds
- Placement of foley catheter
- Result of daily CAM assessment

b. How will the research data be collected, recorded and stored?

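### Duration of delirium is a secondary outcome, but participation ends at first delirium and the plan does not say whether CAM results are recorded after onset or how duration is computed

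*Combined protocol and SAP*

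**What the plan says.** Section V.12 (Statistical Considerations) names three secondary outcomes: risk factors for incident delirium, "Duration of delirium by study group" and "Hospital length of stay".

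Section V.3 (Research Plan) has floor nurses perform the Short CAM twice daily on study subjects. On reaching the endpoint it states: "If the primary end point of delirium is reached, the subject will have completed the study, participation will be over". Study drug stops at the same moment. The section describes routine nursing CAM at the hospital as once daily, except on Verdi 4 West, where every patient has it twice daily. It also says that the causes of delirium will be taken from the chart.

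Other sections bear on data collection:

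- Section V.10 (Minimizing Risks): "The investigation team will review all patients, in EPIC or in person twice per day".
- Section VIII, item a, lists among the data to be collected "Result of daily CAM assessment", "Use of restraints", the number of "prn antipsychotic doses" and length of stay. It attaches no time window to any of them and has no field for resolution or duration.
- Section VII.9 (Process of Consent/Assent): "All subjects will be evaluated by the investigative team twice daily as long as they remain in the study".

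For analysis, Section V.12 gives general tests for continuous variables. It assigns the survival methods to person-days to delirium, and it has an independent geriatrician decide on equivocal CAM results as to whether delirium occurred.

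**The concern.** Duration can be observed only after onset, and Section V.3 places onset at the end of participation. A site that follows that sentence strictly could stop recording CAM results in exactly the subjects who have a duration. A site that reads it loosely would go on using charted CAMs. Either could say that it followed the plan.

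The computation is open as well. Section V.2 describes delirium as fluctuating. If a chart shows a positive, then a negative, then another positive result, the duration depends on whether the episode ends at the first negative, ends at the last positive, or is a count of positive days. Nothing chooses between these, and nothing covers subjects still delirious at discharge or death. Two analysts could derive different durations from the same chart, and the rule could be settled after the data have been seen.

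**Working it through.** **1. The plan's own figure.** Inputs from Section V.12: control incidence 30%, treated incidence 21%, two-sided 5% level, 80% power, 1:1 allocation. With mean proportion p̄ = (0.30 + 0.21)/2 = 0.255, the Fleiss formula without continuity correction is

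n per arm = [1.960·√(2·0.255·0.745) + 0.842·√(0.30·0.70 + 0.21·0.79)]² / (0.30 − 0.21)² = 366.99, rounded up to 367.

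This reproduces the stated 367 per group and 734 in total; power at 367 per arm is 80.0%. (With continuity correction the result is 389, so the correction was not used.) No figure is given for duration.

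**2. How many subjects have a duration.** At the planned rates:

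- placebo: 367 × 0.30 = 110.1
- melatonin: 367 × 0.21 = 77.1
- total: about 187; 187/734 = 25.5%

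Section V.2 quotes an incidence of 11 to 42% in general hospitalizations. Taking that range as the control rate, with the same 30% relative reduction, is an assumption made here to show the spread:

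- low end: 367 × 0.11 + 367 × 0.077 = 40.4 + 28.3, about 69 (9.4% of 734)
- high end: 367 × 0.42 + 367 × 0.294 = 154.1 + 107.9, about 262 (35.7% of 734)

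These are counts of subjects who have a duration. They do not measure bias or lost data.

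**3. The sections side by side.**

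| Question | What the document gives |
|---|---|
| Is duration an outcome? | Yes, Section V.12 |
| When does participation end? | At first delirium, Section V.3 |
| Are CAM results recorded after onset? | Not stated. Section VIII lists a daily CAM result without a window; Section V.3 takes causes, not course, from the chart; Section V.10 describes twice-daily review under risk minimization |
| Which CAMs are assured after participation ends? | Routine only: once daily, and twice daily on Verdi 4 West, Section V.3 |
| How is duration computed? | Not stated. Section V.12 gives tests but no definition of the quantity tested |
| How are subjects still delirious at discharge or death handled? | Not stated |

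**4. Effect of ward frequency.** Section V.3 allocates 1:1 in permuted blocks, and Section VII.5 says that the team is blinded. The number of routine readings on a ward therefore does not depend on treatment. Unequal frequency makes recorded duration noisier, but gives no mechanism that favours one arm.

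**The case against.** The strongest reply is that chart data after onset are evidently meant to be collected. Section V.3 plans to extract causes of delirium from the chart, which concerns subjects who are already delirious. Section VIII lists a daily CAM result, restraints and as-needed antipsychotic doses. Length of stay, itself a secondary outcome, cannot be completed at onset. On this view participation means study drug and bedside involvement, and ending it does not end abstraction. The sentence in Section VII.9 adds little: it concerns consent and capacity, and it governs the investigative team, whereas floor nurses perform the CAM.

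Most of this stands. A reader might infer from Section V.3 that collection stops at onset and that duration cannot be measured. The document does not support that: it ends participation, does not say that abstraction ends, and routine CAMs would still be charted. A reader might also infer that ward differences in CAM frequency bias the comparison between arms. They do not do so by design, for the reason given in the working, and a once-daily reading is available on every ward.

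What the reply does not supply is a statement that CAM results are recorded after onset, or a definition of duration. Both have to be guessed.

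**Conclusion.** The point holds as a conflict between sections together with a missing definition, and it should be fixed. A listed secondary outcome has no stated data source after onset and no computing rule. It concerns about 187 of 734 subjects, assuming that the planned 30% and 21% are realised and enrolment reaches 734.

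The primary outcomes are settled by the time of onset, so neither they nor the sample size is affected.

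A reader might want to set the result beside the shorter duration of delirium that the Section V.2 table notes for the multicentre hip-surgery trial, and to object that here duration is observed off study drug. The document does not say whether drug continued after onset in that trial and proposes no such comparison, so nothing is concluded from it.

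The data-collection grid and the consent form are not in the file and may say more about recording after onset.

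**What to change.** **Section V.3.** Separate the end of participation from the end of chart recording, for example: *For subjects who reach delirium before hospital day 15, participation and study drug end as now written. Charted Short CAM results continue to be abstracted until discharge or death, except for subjects who withdraw or who decline consent on regaining capacity.* Bring Sections V.10, VII.9 and VIII into line, and give the CAM item in Section VIII its time window.

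**Section V.12.** Define duration by one rule on all four wards. One workable choice is the number of hospital days, from onset to discharge or death, with a positive result on one pre-specified daily charted CAM reading. Counting positive days handles recurrence without a separate resolution rule. Because the count is cut off at discharge or death, report by arm how many subjects were still positive at each. Label the comparison among delirious subjects descriptive, because that subset forms after randomisation.

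If this is not wanted, delete the outcome.

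**Cost.** Extra chart abstraction after onset for about 187 subjects (69 to 262 over the range in the working). No new bedside assessment is needed, since at least one CAM a day is already routine. Second readings on Verdi 4 West go unused for this outcome, which loses some information on a fluctuating condition. Consent wording needs attention only if the form does not already cover continued abstraction. No change to when study drug stops is proposed.
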